3.3 Special Populations

No special populations, including adults unable to consent, individuals who are not yet adults, pregnant women, or prisoners, will not be included in this study.

Table 1.

Inclusion Criteria

1. Female
2. Age 21 or older
3. Diagnosis of early-stage (Stage 0-IIib), hormone receptor + breast cancer

4. Within 1 week-36 months of starting adjuvant endocrine therapy
5. Ability to read and respond in English
6. Eastern Cooperative Oncology Group (ECOG) performance status ≤ 2
7. Currently taking adjuvant endocrine therapy (i.e. if took recent break, has taken within the past 2 weeks)
8. Completed primary treatment (i.e., chemotherapy, surgery, and/or radiation) for early-stage breast cancer
9. Indicates a score ≥ 4 on one of the three NCCN adapted distress thermometer study screening questions

Exclusion criteria

1. Uncontrolled psychosis, active suicidal ideation, or psychiatric hospitalization within the past year
2. Cognitive impairment that prohibits participation in the study
3. Enrollment in a different clinical trial for breast cancer
4. Current participation in formal group psychotherapy or other psychosocial intervention trial
5. Undergoing primary treatment for other cancer (i.e., advanced stage cancer)

4.0 Study-Wide Number of Subjects

We propose a four-center run-in period (n=5) and randomized-controlled trial (n=100) of an evidence-based telehealth intervention for a total of 105 BCS taking AET. Our original accrual goal for the RCT was 75, but due to successful enrollment and additional time for conducting the study, we decided to expand accrual to 100 in order to increase our ability to detect group differences in secondary outcomes.

5.0 Study-Wide Recruitment Methods

5.1 Recruitment and Enrollment Procedures

The following recruitment procedures will be executed by the lead site, MGH Boston, at all MGH-affiliate study sites. The three MGH-affiliate sites will not have any responsibilities regarding recruitment or enrollment. All study sites will be open through the DF/HCC IRB as the IRB of record.

Participants will be recruited through the following three methods:

- **EHR Screening:** As detailed above (Section 3.1), study staff will screen the MGH Center for Breast Cancer clinic schedules at the MGH Boston, MGH Northshore, MGH Waltham, and Newton-Wellesley satellite site for potentially eligible patients (under the use of a HIPAA waiver, submitted to the DF/HCC IRB). If a study staff member is attempting to recruit a potentially eligible patient through an affiliate site, they will utilize the study screening and telephone scripts (Appendices 30.3 & 30.4)
- **The Partners Rally Recruitment Portal:** Study staff will submit a recruitment advertisement to the Partners Rally Recruitment Portal (advertisement detailed in Appendix 30.5). Through this portal, interested and potentially eligible patients will be able to send their contact information to the study team. The study team will then reach out to interested patients and use the study screening and telephone scripts to assess fit and eligibility for the study (Appendices 30.3 & 30.4).
- **Provider & Self-Referral:** Patients may be referred to contact the study staff by receiving a study flyer (Appendix 30.6), seeing a study flyer posted in-clinic, or by hearing about the study by an oncology provider. Study site-PIs may also consent patients for the study. If a patient reaches out to the study staff, the study team will use the study screening and telephone scripts to assess fit and eligibility for the study (Appendices 30.3 & 30.4).

For patients meeting initial eligibility criteria and with clinician approval, trained study staff will approach the patient at their clinic visit to explain the study and conduct the informed

consent discussion. Study staff will use Appendix 30.1 to notify the patient's clinician of the intended approach. The study staff will initially introduce the study to patients and ask if they are currently taking their AET. If the patient indicates that they are not interested in the study, study staff will collect the reason for refusal, for the purposes of documentation and future study reporting. If the patient indicates that they are interested in the study and are currently taking their AET, the study staff will screen the potentially eligible patient using the study staff screening script (Appendix 30.3). The brief screening questions are intended to assess the fit of the patient for the study. The participant will screen in to the study if she indicates an answer of 4 or above on any of the three brief screening questions. If a patient screens out of the study, study staff may ask the patient for permission to re-approach her some point in the future, as distress and adherence challenges may come and go at different points throughout the course of the medication. If the patient screens in, she will be presented with a detailed, HIPAA-compliant consent form to be signed by each participant following explanations by study staff. The consent form will include all of the study procedures, information about potential risks and benefits of participation, and information regarding who they can contact for further questions (PI: [name]). It also will state that participation is voluntary, participants can refuse to answer any questions, participants can withdraw from the study at any time, and study participation is in no way related to their medical care. If a participant is unable to be approached in-person or consented in-clinic due to external factors, such as lack of clinic space or patient time constraints, the study team may reach out to potential participants over the phone. Prior to initiating phone contact, the study team will utilize the same provider email to assess if the provider has any reservations about the study staff contacting the patient (Appendix 30.1). If the patient does not have an upcoming appointment in clinic, study staff may call the potentially eligible patient using the recruitment phone script and screening script to gauge interest and eligibility (Appendices 30.3 & 30.4). Study staff will not call more than three times total or leave more than two voice messages (Appendix 30.7). If the patient expresses interest and screens in, the study team will begin the electronic informed consent (EIC) process outlined in Section 27.0.

5.2 *Participant Communication*

Study staff will ask for preferred participant communication methods upon time of approach. Participants will fill out the Participant Locator Form (Appendix 30.12) to indicate best contact and backup contacts. Potential communication includes in-person, by phone, email, or SMS Text Messaging. Phone and email communication have been successful strategies to communicate with patients in prior psychosocial studies, and email templates intended for study use can be found in Appendix 30.14.

SMS Messaging. Participants may elect to provide a personal mobile phone number and provide permission to receive SMS messages via an online service (GoogleVoice) regarding the study that the study staff will monitor. Before doing so, participants will be informed of the limitations of using GoogleVoice, particularly emphasizing that it is not HIPAA-compliant and thus does not offer protection over their personal health information. Additionally, participants will be informed that this phone number is not monitored regularly and should not be used for urgent or emergency purposes. Participants will be advised that, in the case of an emergency, they should contact their care team or emergency services. In the event participants still prefer the use of text messaging, study staff will send brief messages containing limited information regarding scheduling, reminders, and follow-up. Participants will be provided with the number for SMS study-related communications. Study staff will follow the templates as outlined in Appendix 30.13 for SMS communication. Under the discretion of trained study staff and extenuating circumstances, study staff may stray from the following templates to address scheduling/reminder situations not covered by the message templates. Under no circumstances

will study staff ever screen or discuss personal medical history, exchange personal health information, or other sensitive information via SMS message. If a participant introduces sensitive information, including but not limited to the examples just listed, into a SMS message conversation, the study staff member will direct the participant to call them to discuss it further over the phone.

Send Secure Email. Participants will be provided with the Partners Privacy language regarding encrypted emails and given the opportunity to opt-out of Send Secure emails. In previous psychosocial studies, participants have articulated difficulties with accessing encrypted emails and prefer the option to opt-out of such method of encrypted communication. Further procedures on this opt-out process can be found in Section 27.0 on Electronic Informed Consent.

6.0 Multi-Site Research

6.1 Multi-Site Study Conduct

This study will be conducted at MGH Boston, lead site, and at three MGH satellite sites, Newton-Wellesley Hospital, MGH North Shore, and MGH Waltham. All affiliate sites are on record by the DF/HCC IRB. As detailed in Section 5.0, the study staff at MGH Boston will maintain full responsibility of recruitment and enrollment at MGH Boston and at the MGH-affiliate sites. The MGH Boston study team will communicate with providers at Newton-Wellesley Hospital, MGH North Shore, and MGH Waltham regarding permission to approach patients over the phone, as detailed in section 3.0, and on the progress of the study or any protocol updates. Site-PIs and peripheral study staff at the satellite site may assist with referrals but that is the extent of their role in study conduct. All participants will be registered and enrolled on OnCore through MGH Boston, regardless of where a participant's primary oncologist is located. All participants will complete the intervention and all study procedures through study staff at MGH Boston. A HIPAA waiver was submitted to the DF/HCC and authorization approved for all sites to which the study is open.

6.2 Multi-Site Communication

Study staff at the lead site will periodically communicate via phone or email with the satellite site to update sites on study progress or any modifications to study protocol.

6.3 Multi-Site Confidentiality

All study data will be stored and maintained by study staff at the lead study site, MGH Boston. There will be no transmission of study data (e.g., study assessments, exit interview transcripts) from MGH-affiliate sites to MGH Boston. As detailed above, MGH Boston study staff will be responsible for all recruitment and enrollment, including the completion and storage of all participant and study data. This study does not involve any collection of participant specimens.

6.4 Institution Change of Previous Study Member

[name] is a predoctoral psychology trainee in the University of Miami Department of Psychology. [name] was previously engaged in this research study as the primary clinical research coordinator of the study (e.g., recruitment, enrollment, and completion of participant study interviews) from September 2017 to June 2019, at which time she moved to the University of Miami. [name] will assume PI duties at the MGH Cancer Center while [name] role will be to conduct research activities (data interpretations and discussions) at the University of Miami. [name] research activities will also be monitored by [name], a PI and faculty member at the University of Miami. All data activities will be completed with deidentified participant transcripts for qualitative analysis under the

direct supervision of [name] and [name] and will be for use only by [name] under [name] supervision at the University of Miami.

7.0 Study Timelines

Table 2 depicts the expected overall study timeline:

Time Point	Study Procedure
Months 0-6	
• Finalize and submit Institutional Review Board application for approval• Train study staff in study procedures, recruitment, and data collection• Conduct run-in period (n=5) to refine study procedures and intervention
Months 7-33	
• Enroll and randomly assign up to 100 patients to receive either the STRIDE intervention vs. the medication monitoring plus standard care control• Weekly-meetings of study staff to review study progress and address any study issues
Months 34-36	
• Complete data analysis and submit manuscripts• Prepare and submit grant proposal for large-scale randomized trial

Each subject will be enrolled for approximately 24 weeks total.

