This will be the first study to develop and test an evidence-based intervention that is flexible, portable, and tailored to address AET adherence barriers unique to BCS. The proposed strategy implements a mixed-methods design based on the ORBIT model,¹ integrates a comprehensive conceptual framework, adapts an established, evidence-based treatment, and employs novel technologies in the following three ways: 1) Tailored intervention content. 2) Videoconferencing. The use of tele-mental health ZOOM technology limits barriers to treatment such as cost, time, and travel, thereby increasing access to behavioral health interventions.⁸ We will extend the use of videoconferencing to BCS reporting difficulty managing their AET. 3) Objective, electronic measurement. Since self-report methods tend to yield overestimates of adherence,⁹⁻¹² We will use the Medication Event Monitoring System (MEMS¹³) in addition to self-report measures. Thus, this study employs existing technologies in a novel setting to model longitudinal change in AET adherence in the intervention and control groups.¹³

Specific Aims

1. **Primary Aim.** To examine the feasibility and acceptability of a tailored, small-group, Telehealth intervention (STRIDE) compared to a medication monitoring control for survivors of breast cancer taking AET.

Hypothesis 1: The study will be feasible, defined by recruitment (enrollment rate > 50%), retention (follow-up assessment completion rate > 70% of all participants who complete baseline) and attendance (attendance rate of at least 70% of participants completing at least 4 of 6 sessions [67%]).

Hypothesis 2: The study will be acceptable demonstrated by >75% of participants reporting average satisfaction scores greater than the scale's mid-point (Client Satisfaction Questionnaire).

2. **Secondary Aim:** To assess effects of the STRIDE intervention on adherence to AET, symptom distress, and satisfaction with AET.

Hypothesis 2: We hypothesize that participation in the STRIDE intervention will be associated with an increase in adherence and satisfaction with AET and a decrease in symptom distress at 12-weeks compared to the medication monitoring control, and that these improvements will maintain at 24-week follow-up.

3. **Exploratory Aims:**

- a. To assess the effects of the STRIDE intervention on several psychosocial constructs, exploring potential mediator and moderators of the intervention.

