Rationale: Although we considered an attention-matched condition to control for nonspecific intervention effects, we decided against this approach because medication monitoring is likely to improve adherence alone.⁵² Additionally, requesting participation in a placebo intervention adds undue burden to BCS who are coping with emotional and physical sequelae. Finally, an attention control should only be employed if attention would affect the primary outcome. Since no data suggest that attention would improve AET adherence, an attention control would be an added expense and unethical.⁵² Finally, participants who identify as part of a racial/ethnic minority population will be offered the opportunity to participate in a qualitative exit interview to provide feedback on the STRIDE study.

Retention. Strategies to promote retention will include accurate explanations of study expectations during the recruitment process,⁵³ collection of locator information and a secondary contact (Appendix 3.12), a phone check-in to ensure use of MEMS Caps, branding of study materials for project identity, and reimbursement for time (\$20/assessment). Intervention participants will receive a text reminder one day prior to the scheduled ZOOM session (See Section 5.2 detailing Participant Communication).

9.3 *Study Instruments*

The following questionnaires have been specifically selected to reflect the theoretical intervention targets and aims of the study. All participants will complete the baseline questionnaires within four weeks of documented informed consent. If a participant does not complete the baseline questionnaires within this timeframe, she will be re-screened and re-consented, restarting the four-week window. Follow-up assessments will be completed at 12-week (+/- 2 weeks) and 24-week (+/- 2 weeks) from time of baseline completion (Appendix 30.16) Table 3 details the schedule for administering all study instruments. Patient assessments can be found in Appendix 30.16. We anticipate that 15-20% of 12-week assessments will be out

of window for intervention participants, given the occasional delay of coordinating multiple patients' schedules to arrange the intervention groups.

Instrument/Measure:	Screening	Baseline (4-week window from consent)	12-weeks post-baseline (+/- 2-week window)	*24-weeks post-baseline (+/- 2-week window)
Chart review	X			
Adapted NCCN Distress Thermometer	X			

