30.5 Partners Rally Recruitment Advertisement

Headline: STRIDE: Symptom-Targeted Randomized Intervention for Distress on Endocrine Therapy

Summary (240 characters): If you were diagnosed with breast cancer and are currently taking a hormonal therapy, you may be eligible to participate in this research study. Participants are randomized to complete a 6-week, small-group, virtual intervention.

Project Title: Symptom-Targeted Randomized Intervention for Distress and Adherence to Adjuvant Endocrine Therapy (STRIDE) among Breast Cancer Survivors: A pilot feasibility trial

Categories: Breast Cancer, Cancer, Medicines

Project Image:

CT.gov Identifier: To be assigned

Funding Source: NIH

Institutions conducting research: MGH, Newton-Wellesley, MGH North Shore, MGH Waltham

IRB Organization: DF/HCC Dana Farber Cancer Institute

Recruitment start date: 2/1/2019

Recruitment end date: 5/1/2022

What are you studying?

We are studying the feasibility and effectiveness of a tailored program for women currently taking hormonal therapy for breast cancer to reduce distress and improve side effect management and adherence.

Why is it important?

A variety of challenges can arise around taking hormonal therapy, which can interfere with daily living and ability to take the medication. This program will allow women to explore and manage these concerns in a small-group with other breast cancer survivors and a cancer center clinician.

STRIDE

Symptom-Targeted Randomized Intervention for Distress on Endocrine Therapy

The MGH Cancer Outcomes Research Program is conducting a research study to support women taking a hormonal therapy after breast cancer treatment.

If you:

- ❖ Are at least 21 years old
- ❖ Have completed treatment for breast cancer
- ❖ Are currently taking and within 3 years of starting medication, such as Tamoxifen, Arimidex, Letrozole, Exemestane

You may be eligible to participate in a small-group, virtual intervention to manage side effects, decrease distress, and improve adherence to hormonal therapy.

If you would like to learn more about this research study, please tell your oncologist or contact the study coordinator, [name] or [name], at **[contact]** or at **[contact]** or **[contact]**.

Thank you for considering our research study! You will be helping us gather important information about a program that may help other patients in the future.

CANCER
OUTCOMES
RESEARCH

MASSACHUSETTS
GENERAL HOSPITAL
CANCER CENTER

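### Table 2 leaves no follow-up time between the last randomisation (month 33) and the analysis (months 34-36), although the last assessment is due 24 weeks after baseline

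*Combined protocol and SAP*

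**What the plan says.** Table 2 (Section 7.0) has three blocks. Months 0-6 cover approval, training and the run-in. Months 7-33 are given to this activity: "Enroll and randomly assign up to 100 patients to receive either the STRIDE intervention" or the control, with weekly staff meetings. Months 34-36 are given to "Complete data analysis and submit manuscripts" and to preparing the next grant application. No row covers follow-up.

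Directly below the table, the protocol says: "Each subject will be enrolled for approximately 24 weeks total". Section 9.3 fixes the clock: "Follow-up assessments will be completed at 12-week (+/- 2 weeks) and 24-week (+/- 2 weeks) from time of baseline completion". It also says: "All participants will complete the baseline questionnaires within four weeks of documented informed consent". Section 9.1 stratifies randomisation by the HADS score taken at baseline, so baseline comes before randomisation.

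Three uses of the follow-up data matter here:

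- The secondary hypothesis (Specific Aims and Section 11.1) is that gains seen at 12 weeks persist at 24 weeks.
- Section 8.2 compares MEMS adherence over the whole 24-week period.
- The Primary Aim defines "retention (follow-up assessment completion rate > 70% of all participants who complete baseline", without saying whether the 12-week assessment, the 24-week assessment or both must be completed. Section 11.1 does not name a time point either.

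The recruitment advertisement (Appendix 30.5) gives a start date of 2/1/2019 and "Recruitment end date: 5/1/2022".

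**The concern.** Read literally, the schedule moves from the last randomisation to the analysis with no interval, while each woman needs about five and a half months to reach her last assessment. The two statements stand in the same section and cannot both hold if randomisation runs to month 33.

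If the table were followed as written, the latest entrants would be analysed before week 24. The maintenance comparison would lose them and their MEMS records would stop short. Section 11.2 says that the analyses will focus on completers, so women could be set aside as non-completers purely because of the calendar. No section sets a data cut-off, or says that the analysis waits for the last visit.

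**Working it through.** **The plan's own figures.** The documents do not state how many women will have 24-week data, so there is no such figure to reproduce. The nearest one is in Section 11.1: 80% anticipated retention among 80 women, with an exact one-sided 95% lower limit of 71%. For 64/80 the Clopper-Pearson limit is 71.2%, which agrees. Only the 80% is used below.

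**Inputs**

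- Randomisation window: months 7-33 inclusive = 27 months (Table 2).
- Analysis window: months 34-36 = 3 months (Table 2).
- Last assessment: 24 weeks after baseline, at latest 26 (Section 9.3).
- Weeks per month: 365.25/7/12 = 4.348. So 24 weeks = 5.52 months and 26 weeks = 5.98 months.
- Assumption: uniform accrual over the 27 months.
- Assumption: no gap between baseline completion and randomisation. The documents give none, and a gap would bring each finish slightly earlier.

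**Last participant (no accrual assumption needed)**

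- 33 + 5.52 = month 38.5
- 33 + 5.98 = month 39.0

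Both fall after month 36.

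**Share without 24-week data.** The formula is (follow-up in months - months elapsed since the end of month 33) / 27.

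| Cut-off | At 24 weeks | At 26 weeks |
|---|---|---|
| Start of month 34 | 5.52/27 = 20.4% | 5.98/27 = 22.1% |
| End of month 36 | (5.52 - 3)/27 = 9.3% | (5.98 - 3)/27 = 11.0% |

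Counting the window as 26 months (33 minus 7) changes these little: 21.2% and 23.0% at the start of month 34, and 9.7% and 11.5% at the end of month 36.

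**Retention, if judged at week 24 with women not yet due counted as incomplete, and 80% true completion**

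- Start of month 34: 0.80 x (1 - 0.204) = 63.7%; 0.80 x (1 - 0.221) = 62.3%
- End of month 36: 0.80 x (1 - 0.093) = 72.6%; 0.80 x (1 - 0.110) = 71.2%

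**Retention, if judged at week 12.** 12 weeks = 2.76 months, so 2.76/27 = 10.2% are not yet due at the start of month 34 and none at the end of month 36. At the +2-week limit, 14 weeks = 3.22 months and (3.22 - 3)/27 = 0.8% are still not due at the end of month 36.

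**Latest randomisation that lets everyone finish by the end of month 33**

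- 33 - 5.52 = month 27.5
- 33 - 5.98 = month 27.0 with the window

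**Advertised dates.** From 2/1/2019 to 5/1/2022 is about 39 months. That is longer than the 27-month randomisation window and longer than the whole 36-month table. Month 0 has no calendar date, so the two cannot be aligned more closely.

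**The case against.** The best defence is that Table 2 is an outline of expected timing. The months 7-33 row also omits intervention delivery and every assessment, so it may be shorthand for the conduct of the whole trial. The target is up to 100, and accrual could finish early. The last row speaks of completing the analysis; no section locks the database at month 34 or stops follow-up at month 33. Section 4.0 mentions additional time for conducting the study, and the advertised recruitment is longer than the table, so month 36 may not be a hard stop.

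Much of this stands, and it limits the size of the problem. It does not remove the contradiction. The row names enrolment and random assignment specifically, and no section gives an earlier accrual close or a later cut-off. The advertised 39 months fits neither reading of the table.

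Three stronger readings are tempting, and the documents do not support them:

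- **A fifth of the women cannot have 24-week data.** That needs both uniform accrual and a cut at the start of month 34. Front-loaded accrual lowers the share and back-loaded accrual raises it. If follow-up continues during months 34-36, the share out of reach is about 9-11%.
- **The retention criterion would be missed.** Retention names no time point, and nothing says that women not yet due count as lost. Even on that pessimistic count, the observed rate at month 36 is 71-73%, above the 70% threshold. At month 34 about 62 of 100 would have completed, which still meets the aim in Section 3.2 of at least 60 completing.
- **The last participant finishes at month 40.** This adds the four-week consent-to-baseline allowance after randomisation. Because the baseline HADS is needed to stratify, that interval has already passed when a woman is randomised.

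**Conclusion.** The point holds as a minor scheduling contradiction. Table 2 provides no follow-up after the last randomisation, and a woman randomised at the end of month 33 would finish at about month 38.5-39.0, beyond the 36-month schedule. That part rests only on the protocol's own dates and on baseline and randomisation falling close together.

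The size depends on assumed uniform accrual over 27 months: about 20-22% without 24-week data at the start of month 34, and about 9-11% at the end of month 36 if follow-up continues. The maintenance comparison and the 24-week MEMS record are directly exposed. The effect on retention is conditional. Judged at week 24 with women not yet due counted as incomplete, and with 80% true completion, about 62-64% would be observed at month 34 and 71-73% at month 36. Judged at week 12, the shortfall is about 10% at month 34 and essentially nil by month 36.

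**What to change.** - Add a follow-up period to Table 2. Either close randomisation by about month 27, or keep it open to month 33 and move the final analysis to about month 39.
- State that retention and the 24-week endpoints are analysed only after the last participant's 24-week window has closed.
- Say which follow-up assessment (12-week, 24-week or both) defines retention.
- Reconcile the recruitment dates in Appendix 30.5 with Table 2, and give month 0 a calendar date.

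The cost is a few lines of timeline and definition wording, plus either a later analysis or an earlier close of accrual. No design element or analysis method changes.
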